For assessing drug-induced liver injury (DILI), the Roussel Uclaf Causality Assessment Method (RUCAM) can be used as a valid tool in which factors like time to onset of ALT/AST elevation, response to drug dechallenge, response to drug rechallenge, evaluation of alternative causes etc. are collectively evaluated and scored to determine the possibility of attribution to ALT/AST elevation [54]. For axitinib, early-onset, prompt recovery from ALT/AST elevation in response to axitinib interruption without confounding by corticosteroid treatment, suggests the event is likely associated with axitinib after excluding other alternative explanations). A positive rechallenge, i.e., ALT/AST recurrence following retreatment will provide further support for its attribution. The determination of immune-related hepatitis mostly relies on the exclusion of other causes including axitinib. If the initial ALT/AST elevation does not respond rapidly to axitinib interruption but responds to subsequent corticosteroid treatment, it suggests a potential for immune-mediated hepatitis by pembrolizumab. It should be borne in mind that not all immune-mediated hepatitis will respond to corticosteroid treatment.

Guidelines on causality evaluation and management for ALT/AST elevations of > 3xULN during axitinib / pembrolizumab combination treatment are outlined in the following:

1. **Promptly interrupt both study drugs and any other suspected concomitant medications.** Note, concomitant medications include over-the-counter (OTC) and herbal medications and supplements.
2. **Adequately monitor liver enzymes and liver function changes** - Liver enzyme tests should include ALT, AST, and ALP; liver function tests should include total bilirubin, and PT or INR. Bilirubin fractionation should be performed if total bilirubin is $\geq 2xULN$ or is clinically significant as elevated conjugated bilirubin (i.e., direct bilirubin) reflects liver dysfunction. Liver enzyme tests and liver function tests will be referred, collectively, as liver tests for the rest of this section.
 - a. Repeat liver tests within 24 to 72 hours to confirm the initial observation.
 - b. Continue to monitor liver tests twice weekly, while evaluating other causes, until ALT/AST values are trending down (>10% decrease between sequential assessments) and then monitored weekly until recovered to $\leq 2xULN$ or values are back to baseline.
3. **Decision on initiation of corticosteroid treatment** - While corticosteroid is essential for managing immune-mediated hepatitis, administration of steroids prior to identifying the most likely causes of ALT/AST elevation will confound the causality assessment and impact proper management of the event. Hence the followings are recommended:
 - a. ***Hold steroid initiation*** for ALT/AST elevations that are not associated with signs of clinically significant hepatic dysfunction (i.e., total bilirubin <2xULN and PT/INR <1.5xULN). Continue to monitor with liver tests and clinical symptoms.
 - b. ***Steroid therapy should be initiated if:***
 - i. ALT/AST elevation is associated with signs of clinically significant hepatic dysfunction (i.e., ALT/AST > 3 x ULN concurrent with total bilirubin $\geq 2xULN$ (excluding biliary obstruction) and/or PT/INR $\geq 1.5xULN$) OR,
 - ii. ALT/AST elevation has been persistent (ie, no prompt improvement after axitinib dechallenge) or further increased and without alternative causes identified. Consider observing liver enzyme and function changes for approximately 3 to 7 days prior to making a decision, if subject is clinically stable.
4. **Thoroughly evaluate alternative causes** – The following includes a list of potential alternative causes that should be evaluated and excluded:
 - a. Medical history relevant to the liver event
 - b. History of alcohol use and recent alcohol use
 - c. Serology for hepatitis A, B, C, and E; serology for CMV, EBV

- d. Obstructive hepatic disease
 - e. Cardiac or vascular etiology (e.g., any cause of severe hypoperfusion of the liver, severe cardiac failure)
 - f. Severe systemic infection
 - g. Exposure to other drugs including OTC and herbal medications that are potentially associated to DILI (e.g., statins, acetaminophen etc.)
 - h. Evaluating other causes as appropriate
5. **Decision on axitinib/ pembrolizumab rechallenge** – If initial ALT/AST elevation event is assessed as related to study treatment (*i.e.*, alternative causes were excluded), the decision on rechallenge with one or both study treatments should be based on the outcome of causality assessments (as described above) and the severity of the initial ALT/AST elevation event. Prior to rechallenge with either axitinib or pembrolizumab, initial ALT/AST elevations must recover to $\leq 2 \times$ ULN or to baseline values without signs and symptoms of hepatic dysfunction. See [Table 10](#) for algorithms of decision on axitinib/ pembrolizumab rechallenge after recovery from drug-related ALT/AST elevation.
6. **Severe hepatic events should be promptly managed, including hospital admission and seeking hepatic consultation as appropriate.**

Table 10 Algorithms of decision on axitinib/ pembrolizumab rechallenge after recovery from drug-related ALT/AST elevation

Initial ALT/AST elevation scenario	Rechallenge decision
Scenario 1: ALT/AST > 3 x ULN concurrent with total bilirubin $\geq 2 \times$ ULN (excluding biliary obstruction) and/or PT/INR >1.5xULN (i.e. , ALT/AST elevation with clinically significant signs of hepatic dysfunction)	
 • No rechallenge with either axitinib or pembrolizumab is allowed. Subject should be followed with liver tests until recovery..
Scenario 2: ALT/AST >3-5 x ULN without clinically significant signs of hepatic dysfunction (i.e. total bilirubin < 2xULN and PT/INR <1.5xULN)	
 • Axitinib and pembrolizumab combination can be resumed sequentially with axitinib (at the previous dose) resumed first for 2-3 weeks with weekly liver test monitoring: 
 ○ If no recurrence, consider adding pembrolizumab ○ If with ALT/AST recurrence is >5xULN (i.e., Grade 3 or 4), discontinue axitinib and rechallenge with pembrolizumab ○ If ALT/AST recurrence is >3-5xULN (i.e., Grade 2), dose reduce axitinib then rechallenge or discontinue axitinib and rechallenge with pembrolizumab • Permanently discontinue pembrolizumab if ALT/AST recurrence is >5x ULN or interrupt pembrolizumab if ALT/AST recurrence is >3 to 5x ULN after its rechallenge and manage per Section 5.2.2.1.

Initial ALT/AST elevation scenario	Rechallenge decision

Scenario 3: ALT/AST >5 to 10× ULN without clinically significant signs of hepatic dysfunction (i.e., total bilirubin < 2× ULN and PT/INR <1.5× ULN). Consultation with Sponsor medical monitor is required prior to rechallenge.
	
 • If initial event is likely to be immune-mediated by pembrolizumab (i.e., no prompt decrease in ALT/AST after axitinib interruption and required initiation of steroid treatment as described in item 3b of this section, responded to steroid treatment, and no alternative explanations): 
 ○ discontinue pembrolizumab and rechallenge with axitinib as monotherapy (at same dose) • If initial event is likely related to axitinib (e.g. prompt recovery after axitinib interruption without confounding by steroid treatment), first rechallenge with axitinib (at reduced dose) for 2 to 3 weeks with weekly liver test monitoring: 
 ○ If no recurrence, add pembrolizumab ○ If ALT/AST recurrence is >5× ULN, permanently discontinue axitinib and rechallenge with pembrolizumab ○ If ALT/AST recurrence is >3 to 5× ULN, dose reduce axitinib then rechallenge or discontinue axitinib, depending on the reoccurrence of the events and rechallenge with pembrolizumab • Permanently discontinue pembrolizumab if ALT/AST recurrence is >5× ULN or interrupt pembrolizumab if ALT/AST recurrence is >3 to 5× ULN after its rechallenge and manage per Section 5.2.2.1.

Scenario 4: ALT/AST > 10 × ULN without clinically significant signs of hepatic dysfunction
 
Consultation with Sponsor medical monitor is required prior to rechallenge
	
 • If initial event is likely to be immune-mediated by pembrolizumab: 
 ○ discontinue pembrolizumab and rechallenge with axitinib as monotherapy • If initial event is likely related to axitinib and unlikely due to pembrolizumab: 
 ○ Rechallenge with pembrolizumab monotherapy • If event is potentially related to a contribution of both drugs (such as upfront steroid use with improvement along with axitinib interruption), subject may be rechallenged with axitinib at reduced dose: 
 ○ If no recurrence, continue with axitinib monotherapy ○ If ALT/AST elevation recurs, discontinue axitinib and may be rechallenged with pembrolizumab • Permanently discontinue pembrolizumab if ALT/AST recurrence is >5× ULN or interrupt pembrolizumab if ALT/AST recurrence is >3 to 5× ULN after its rechallenge and manage per Section 5.2.2.1. • Permanently discontinue axitinib if ALT/AST recurrence is >5× ULN or interrupt axitinib if ALT/AST recurrence is >3 to 5× ULN and rechallenge with reduced dose.

Note: 1. Subject should have weekly monitoring with liver tests (i.e., liver enzyme and function tests) for 2-3 weeks after each drug rechallenge. 2. If both study drugs are discontinued due to a hepatic event, subjects should be monitored until AE resolution as per protocol and continue imaging and survival follow-up as per protocol. 3. Events under Scenario 1, 3, and 4 must be reported to the Sponsor as Events of Clinical Interest (see Section 7.2.3.2 for details). 4. Liver tests include liver enzyme (ALT, AST, and ALP) and liver function (bilirubin and PT/INR) tests.
 
Abbreviations: ALP = alkaline phosphatase; ALT = alanine aminotransferase; AST = aspartate aminotransferase; INR = international normalized ratio; PT = prothrombin time.
	

5.2.2.4 Dose Modification Guidelines for Adverse Events Potentially Associated with Sunitinib Treatment

The study is using the label-recommended dose and schedule for RCC (50 mg QD 4 weeks on, 2 weeks off). Dose interruption and/or dose modification in 12.5-mg increments or decrements is recommended based on individual safety and tolerability, as per label recommendations. If 50 mg QD cannot be tolerated, the next dose level is 37.5 mg QD. Dose can be further reduced to 25 mg QD. Once toxicity has been alleviated, doses should be re-escalated stepwise to 37.5 mg and then 50 mg. Subjects requiring a dose below 25 mg QD should be permanently discontinued from study treatment. During each 6-week cycle, subjects will be off of treatment for 2 weeks. If an additional dose interruption for more than 2 weeks is required, the Sponsor should be consulted (Table 11).

Table 11 Dose Modification Guidelines for AEs Potentially Associated with Sunitinib Treatment

Toxicity	NCI CTCAE Grade	Sunitinib
Hypertension See Section 5.6.2 for monitoring/management of treatment-related hypertension.	SBP \leq 150 mm Hg and / or DBP \leq 100 mm Hg	Continue at the same dose level Antihypertensive treatment maybe initiated
	SBP >150 mm Hg but < 160 mm Hg and / or DBP >100 mm Hg but < 105 mm Hg	Continue at the same dose level, and institute new or additional antihypertensive medication if not on maximal antihypertensive treatment, or Reduce by 1 dose level if on maximal antihypertensive treatment.
	SBP >160 mm Hg and / or DBP > 105 mm Hg	Hold dose and adjust antihypertensive medication to achieve BP controlled to SBP \leq 150 mm Hg and DBP \leq 100 mm Hg. Resume at the same dose level or 1 level reduced. Note: If sunitinib dosing is temporarily interrupted, subjects receiving antihypertensive medications should be monitored closely for hypotension.
	Recurrent hypertensions following previous dose reduction	Repeat dose interruption and/or dose reduction by one lower dose level. Permanently discontinue if hypertension is severe and persistent despite antihypertensive treatment and dose interruption, or experience hypertensive crisis, transient or permanent neurological deficit related to uncontrolled hypertension.

Toxicity	NCI CTCAE Grade	Sunitinib
Proteinuria	Dipstick negative or 1+	Continue at the same dose level.
	If dipstick shows $\geq 2+$, perform 24-hour urine protein or UPC. Dosing may continue while waiting for test results	
	Urine protein < 3 g/24 hr or UPC < 3	Continue at the same dose level.
	Urine protein ≥ 3 g/24 hr or UPC ≥ 3	Hold until urine protein is < 3 g/24 hr or UPC <3. Restart with 1 dose level lower Permanently discontinue if urine protein cannot reduce to < 3 g/24 hr or UPC <3 after dose reduced to 25 mg daily
Prolongation of QTc Interval:	480 < QTc < 500 msec	Continue study treatment; monitor as clinically indicated.
	QTc ≥ 500 msec	Permanently discontinue and follow-up per protocol.
Diarrhea/Colitis	Grade 1-2	Continue at the same dose level
	Grade 3	Continue and dose reduce by 1 dose level Follow the guidelines as in non-hematologic toxicities
	Grade 4	Follow the guidelines as in non-hematologic toxicities
Hemorrhage /Bleeding: Investigate and document underlying etiology of the bleeding	Grade 1	For hemoptysis, interrupt study treatment and evaluate underlying causes. Resume at the discretion of the investigator. For other Grade 1 hemorrhage/bleeding events, continue at the current dose; monitor as clinically indicated.
	Grade 2	For pulmonary or GI bleed (other than hemorrhoidal bleeding), Permanently discontinue and follow-up per protocol. For other Grade 2 hemorrhage/bleeding events, interrupt study treatment until the AE resolved to \leq Grade 1. Restart at 1 dose level lower
	Grade 3 or 4	Permanently discontinue and follow-up per protocol.
Hyperthyroidism	Grades 1-2	Continue at the same dose level
	Grade 3	Grade 3 toxicities controlled with symptomatic medications, or Grade 3 asymptomatic biochemistry (other than abnormal liver tests) laboratory abnormalities: may continue at the same dose level or reduce by one dose level per Investigator judgment
	Grade 4	Hold until recovery to Grade ≤ 1 or BL. Restart at 1 dose level lower.
Hypothyroidism	All grades	Dose can be continued while thyroid replacement therapy is instituted
Isolated AST/ ALT or bilirubin elevation	Grade 1	Continue at the same dose level
	Grade 2	Hold until recovery to Grade ≤ 1 or BL. Restart at same dose level.
	Grade 3 or 4	Hold until recovery to Grade ≤ 1 or BL. Restart at 1 dose level lower.
	ALT/AST >3xULN concurrent with total bilirubin > 2xULN (excluding Gilbert syndrome)	Permanently discontinue and perform virology and serology tests to evaluate the causes

Toxicity	NCI CTCAE Grade	Sunitinib
Non-hematologic Toxicities, Laboratory Abnormalities and/or Other Drug Related Toxicities suspected to be contributed to sunitinib	Grade 1 - 2	Continue at the same dose level
	Grade 3 or intolerable grade 2	Withhold dose until toxicity is Grade \leq 1 or has returned to BL Resume treatment at the same dose level. ^a If the toxicity recurs with Grade 3 severity (or intolerable Grade 2) at the discretion of the investigator, reduce the dose by 1 level.
	Grade 4	Withhold dose until toxicity is Grade \leq 1 or has returned to BL, then reduce the dose by 1 level and resume treatment, or discontinue at the discretion of the investigator. ^a
		Permanently discontinue sunitinib for: 
 Any life-threatening adverse event. Subjects with the following events: CHF,^b pancreatitis, necrotizing fasciitis, nephrotic syndrome and thrombotic microangiopathy), RPLS, and arterial thrombosis/ ischemia Nausea, vomiting, or diarrhea persist at Grade 3 or 4 despite maximal medical therapy.
Hematologic Laboratory Abnormalities	Grade 1-2	Continue at the same dose level.
	Grade 3	Withhold dose until toxicity is Grade \leq 2 or has returned to BL, then resume treatment at the same dose level. ^c If the toxicity recurs with Grade 3 severity, at the discretion of the investigator, reduce the dose by 1 level.
	Grade 4	Withhold dose until toxicity is Grade \leq 2 or has returned to BL Restart with 1 dose level lower. ^c

^a Subjects who develop Grade 3 hypophosphatemia or Grade 4 hyperuricemia without clinical symptoms may continue study treatment without interruption at the discretion of the investigator.

^b Subjects should be carefully monitored for clinical signs and symptoms of CHF while receiving sunitinib. Assessment of LVEF should be considered as clinically indicated per sunitinib label and standard of care.

^c Subjects who develop Grade 3 or 4 lymphopenia may continue study treatment without interruption. Complicated neutropenia includes duration of Grade 4 longer than 7 days or concurrent fever or infection.

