Serum creatinine OR calculated creatinine clearance (CrCl) ^a Note: GFR can also be used in place of creatinine or CrCl	$\leq 1.5 \times$ upper limit of normal (ULN) OR $\geq 40 \text{ mL/min}$ for subjects with creatinine levels $> 1.5 \times$ institutional ULN
Urine protein	$< 2+$ by dipstick urinalysis If dipstick is $\geq 2+$, then 24 hr urine protein must be $< 2 \text{ g}$, or urine protein creatinine ratio (UPC) must be < 2
Hepatic	
Serum total bilirubin	$\leq 1.5 \times \text{ULN}$ OR Direct bilirubin $\leq \text{ULN}$ for subjects with total bilirubin levels $> 1.5 \text{ ULN}$
AST (SGOT) and ALT (SGPT)	$\leq 2.5 \times \text{ULN}$
Coagulation	
International Normalized Ratio (INR) or Prothrombin Time (PT)	$\leq 1.5 \times \text{ULN}$ unless subject is receiving anticoagulant therapy as long as INR or PT is within therapeutic range of intended use of anticoagulants
ALT (SGPT)=alanine aminotransferase (serum glutamic pyruvic transaminase); AST (SGOT)=aspartate aminotransferase (serum glutamic oxaloacetic transaminase); GFR=glomerular filtration rate;. ^a Creatinine clearance should be calculated per institutional standard.	

11. Female subjects of childbearing/reproductive potential must have a negative urine or serum pregnancy test within 72 hours prior to randomization. If the urine test is positive or cannot be confirmed as negative, a serum pregnancy test will be required.

Note, in the event that 72 hours have elapsed between the screening pregnancy test and the first dose of study treatment, another pregnancy test (urine or serum) must be performed and must be negative in order for subject to start receiving study medication.

12. Female subjects of childbearing potential (Section 5.7.2) must be willing to use an adequate method of contraception as outlined in Section 5.7.2 – Contraception, for the course of the study through 120 days after the last dose of study medication.

Note: Abstinence is acceptable if this is the usual lifestyle and preferred contraception for the subject.

13. Male subjects of childbearing potential must agree to use an adequate method of contraception as outlined in Section 5.7.2- Contraception, starting with the first dose of study therapy through 120 days after the last dose of study therapy.

Note: Abstinence is acceptable if this is the usual lifestyle and preferred contraception for the subject.

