	SBP >150 mm Hg but <160 mm Hg and / or DBP >100 mm Hg but <105 mm Hg	Continue at the same dose level, and institute new or additional antihypertensive medication if not on maximal antihypertensive treatment, or Reduce by 1 dose level if on maximal antihypertensive treatment.
	SBP >160 mm Hg and / or DBP >105 mm Hg	Hold and adjust antihypertensive medication to achieve BP controlled to SBP ≤150 mm Hg and DBP ≤100 mm Hg. Resume at the same dose level or 1 level reduced. Note: If axitinib dosing is temporarily interrupted, subjects receiving antihypertensive medications should be monitored closely for hypotension. The plasma half-life of axitinib is 2-4 hours and BP usually decreases within 1-2 days following dose interruption.
	Recurrent hypertension following previous dose reduction	Repeat dose interruption and/or dose reduction. Permanently discontinue if hypertension is severe and persistent despite anti-hypertensive treatments and dose reduction, or experiencing hypertensive crisis, transient or permanent neurological deficit related to uncontrolled hypertension.
Proteinuria	Dipstick negative or 1+	Continue at the same dose level.
	If dipstick shows ≥2+, perform 24-hour urine protein or UPC. Dosing may continue while waiting for test results.	
	Urine protein <3 g/24 hr or UPC <3	Continue at the same dose level.
	Urine protein ≥3 g/24 hr or UPC ≥3	Hold until urine protein is <3 g/24 hr or UPC <3. Restart with 1 dose level lower Permanently discontinue if urine protein cannot reduce to < 3 g/24 hr or UPC <3 after dose reduced to 2 mg BID
Diarrhea	Grade 1 – 2	Continue at the same does level
	Grade 3	Follow the guidelines as in non-hematologic toxicities
	Grade 4	Follow the guidelines as in non-hematologic toxicities

Toxicity	NCI CTCAE grade	Axitinib
Hemorrhage /Bleeding	Grade 1	For hemoptysis, interrupt study treatment and evaluate underlying causes. Resume at the discretion of the investigator. For other Grade 1 hemorrhage/bleeding events, continue at the current dose; monitor as clinically indicated.
	Grade 2	For pulmonary or GI bleed (other than hemorrhoidal bleeding), Permanently discontinue and follow-up per protocol. For other Grade 2 hemorrhage/bleeding events, interrupt study treatment until the AE resolves to ≤ Grade 1. Restart at 1 dose level lower
	Grade 3 or 4	Permanently discontinue and follow-up per protocol.
AST/ALT with total bilirubin <2xULN and PT/INR <1.5xULN	Grade 1	Continue at the same dose level

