	Grade 2	Hold until recovery to <2xULN or BL. Restart at same dose level.
	Grade 3 or 4	Hold until recovery to <2xULN or BL. Restart at 1 dose level lower.
AST/ALT Elevation with clinically significant hepatic dysfunction (i.e. total bilirubin ≥ 2xULN excluding biliary obstruction or PT/INR ≥ 1.5xULN)		Permanently discontinue and follow-up per protocol. See Section 5.2.2.3.1 for details in evaluating and managing ALT/AST elevations during axitinib/pembrolizumab combination treatment
Hyperthyroidism	Grades 1-2	Continue at the same dose level
	Grade 3	If symptoms can be controlled with symptomatic medications, or if asymptomatic: may continue at the same dose level or dose reduced by 1 dose level per Investigator judgment
	Grade 4	Hold until recovery to Grade ≤ 1 or BL. Restart at 1 dose level lower.
Hypothyroidism	All grades	Axitinib can be continued while thyroid replacement therapy is instituted
Renal Failure or Nephritis	Grade 1-2	Continue at the same dose level
	Grade 3 -4	Hold until recovery to Grade < 2. Restart at 1 dose level lower.

Toxicity	NCI CTCAE grade	Axitinib
Non-hematologic Toxicities, Laboratory Abnormalities and/or Other Drug Related Toxicities suspected to be contributed to axitinib and not considered immune-related	Grade 1 - 2	Continue axitinib at the same dose level
	Grade 3 - 4	Grade 3 toxicities controlled with symptomatic medications, or Grade 3 asymptomatic biochemistry (other than abnormal liver test) laboratory abnormalities may continue axitinib at the same dose level per Investigator judgment. Other Grade 3 toxicities may continue axitinib dose reduced by 1 dose level. Grade 4 asymptomatic biochemistry laboratory (other than abnormal liver test) abnormality may continue axitinib without interruption per Investigator's judgment. Other Grade 4 non-hematologic/laboratory and non-laboratory abnormalities hold treatment until recovery to Grade <2 then, then restart axitinib dose reduced by 1 dose level.
	Grade 3-4 discontinuation criteria	Permanently discontinue axitinib for: 
 • Severe or Grade 3 drug-related AEs that recur • Any life-threatening AEs. • Subjects with the following events will be permanently discontinued: RPLS, arterial thrombosis/ischemia,
Hematologic Laboratory Abnormalities	Grade 1-3	Continue axitinib at the same dose level.

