5.6.2 General Supportive Care Guidelines

Subjects should receive appropriate supportive care measures as deemed necessary by the treating investigator including but not limited to the items outlined below:

- Diarrhea: All patients who experience diarrhea should be advised to drink liberal quantities of clear fluids. If sufficient oral fluid intake is not feasible, fluid and electrolytes should be substituted via IV infusion.
- Nausea/vomiting: Nausea and vomiting should be treated aggressively, and consideration should be given in subsequent cycles to the administration of prophylactic antiemetic therapy according to standard institutional practice. Patients should be strongly encouraged to maintain liberal oral fluid intake.

- Anti-infectives: Patients with a documented infectious complication should receive oral or IV antibiotics or other anti-infective agents as considered appropriate by the treating investigator for a given infectious condition, according to standard institutional practice.
- Anti-inflammatory or narcotic analgesics may be offered as needed. Acetaminophen/paracetamol to a MAXIMUM total daily dose of 2 g is permitted. Daily intake over 2 g is prohibited.
- Patients who need to be on anticoagulant therapy during treatment should be treated with low molecular weight heparin. If low dose heparin cannot be administered, the administration of coumadin or other coumarin derivatives or other anti-coagulants may be allowed; however appropriate monitoring of prothrombin time/International normalized ratio (PT/INR) should be performed.

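### The combination-arm liver rules count as hepatic dysfunction some PT/INR and total bilirubin values that the plan itself accepts for other reasons

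*Combined protocol and SAP*

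**What the plan says.** Eligibility (Section 5.1.2, Table 4). PT/INR must be at most 1.5xULN, "unless subject is receiving anticoagulant therapy as long as INR or PT is within therapeutic range of intended use of anticoagulants". Total bilirubin above 1.5xULN is accepted when direct bilirubin is at or below ULN, and no upper cap on the total is stated. AST and ALT may be up to 2.5xULN at entry.

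On treatment (Section 5.6.2). Low molecular weight heparin is the first choice. If heparin cannot be given, "the administration of coumadin or other coumarin derivatives or other anti-coagulants may be allowed", with PT/INR monitoring.

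Axitinib rules (Section 5.2.2.2, Table 8). The graded liver rows are headed "AST/ALT with total bilirubin <2xULN and PT/INR <1.5xULN". Grade 1 means continuing at the same dose. The next row covers "AST/ALT Elevation with clinically significant hepatic dysfunction (i.e. total bilirubin ≥ 2xULN excluding biliary obstruction or PT/INR ≥ 1.5xULN"). Its grade cell is empty, its action is permanent discontinuation, and it refers to Section 5.2.2.3.1 for detail.

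Combination liver guidance (Section 5.2.2.3.1). This starts at ALT/AST above 3xULN. Item 2 asks for bilirubin fractionation at total bilirubin of 2xULN or more, because it is the conjugated fraction that reflects liver dysfunction. Item 3b(i) starts steroids when "ALT/AST elevation is associated with signs of clinically significant hepatic dysfunction", using the same bilirubin and PT/INR limits above an ALT/AST level of 3xULN. Table 10 Scenario 1 states for such events: "No rechallenge with either axitinib or pembrolizumab is allowed".

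**The concern.** The plan knowingly accepts two laboratory situations, therapeutic anticoagulation and raised total bilirubin with a normal direct fraction. It then uses PT/INR and total bilirubin as markers of hepatic dysfunction without saying how to read them in those subjects. The only exclusion written into the definition is biliary obstruction.

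At stake is permanent loss of axitinib or, above 3xULN, steroid treatment and loss of both drugs, because of a value that the plan had accepted. Another subject with the same ALT/AST value but normal PT/INR and bilirubin would continue or resume. Sites could also apply the rule differently, since some will follow the text and others will discount the anticoagulant effect.

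**Working it through.** The plan gives no figure to reproduce here. The check sets the limits for the same laboratory values side by side.

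**Overlap between what is accepted and what is flagged**

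- PT/INR: the Table 4 waiver is needed only above 1.5xULN. Table 8 and item 3b(i) flag 1.5xULN or more, and Table 10 Scenario 1 flags more than 1.5xULN. Everyone who needs the waiver therefore meets the PT/INR criterion in all three places while PT/INR stays there.
- Total bilirubin: Table 4 accepts values above 1.5xULN with normal direct bilirubin, and the liver rules flag 2xULN or more. The overlap is 2xULN and above. Values above 1.5 but below 2xULN are not flagged.

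**Cases (illustrative values, ALT/AST rise judged potentially drug-related)**

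| Case | Table 8 | Section 5.2.2.3.1 and Table 10 | Same ALT with normal PT/INR and bilirubin |
|---|---|---|---|
| A: PT/INR 2.0xULN in therapeutic range, ALT 2xULN | Graded rows closed; axitinib permanently stopped | Not entered (ALT not above 3xULN) | Grade 1: continue at the same dose |
| B: total bilirubin 2.2xULN, direct at or below ULN, ALT 2xULN | As A | Not entered | As A |
| C: PT/INR or bilirubin as in A or B, ALT 4xULN | Axitinib permanently stopped | Steroids under 3b(i); Scenario 1, neither drug rechallenged | Scenario 2: combination can be resumed sequentially |

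The values in A and B satisfy Table 4 at entry. Case C can arise only on treatment, since 4xULN exceeds the entry limit of 2.5xULN.

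**Two internal mismatches**

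- ALT/AST level: the Table 8 row states none, while the section it refers to starts above 3xULN and both item 3b(i) and Scenario 1 repeat that level. Cases A and B depend on this; case C does not.
- PT/INR cut-off: at exactly 1.5xULN with bilirubin below 2xULN, Table 8 and item 3b(i) flag the subject. Scenario 1 (above 1.5) does not, and Scenarios 2 and 3 (below 1.5) do not fit either.

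**Size**

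Number affected = subjects with a flagged but accepted value at the time × rate of ALT/AST rises judged potentially drug-related.

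The second factor has a rough source. Section 5.2.2.3.1 reports 4 Grade 3 and 4 Grade 2 treatment-related ALT/AST elevations or hepatic dysfunction among 52 Phase 1b subjects: (4 + 4)/52 = 15.4%. Table 10 equates Grade 2 with more than 3 to 5xULN, so this approximates the rate relevant to case C. The first factor appears nowhere in the documents, so the product cannot be computed.

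**The case against.** **Causality and work-up.** Section 5.2.2 applies the tables only to events assessed as associated or potentially associated with the drug, and Table 8 is limited to drug-related events. Above 3xULN, item 4 requires a search for other causes, item 2 requires bilirubin fractionation, and the rechallenge rules apply after alternative causes are excluded. This stands as mitigation: a rise judged unrelated does not enter the row. It does not close the gap. Those steps ask why ALT/AST rose. None asks why PT/INR or bilirubin is raised, and the fractionation result does not feed into the definition. Other Table 8 rows grant investigator judgment expressly; this one does not.

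**ALT/AST level.** It is plausible to carry the 3xULN level into Table 8 from the section it cites. On that reading cases A and B disappear and case C remains. The text does not settle which reading is meant.

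**A small group.** Heparin is preferred. Deep vein thrombosis or pulmonary embolism within 6 months, and several cardiovascular conditions within 12 months, are exclusions. This narrows the group but does not empty it: Table 4 sets no heparin-only condition.

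**Stronger readings that the documents do not support**

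- A reader might infer that a mild ALT/AST rise costs the subject both drugs. The Table 8 row concerns axitinib, and Section 2.1 continues the other compound as monotherapy. Loss of both drugs needs ALT/AST above 3xULN.
- A reader might infer that hepatic events of clinical interest are not comparable between arms, because the sunitinib row in Table 11 ("ALT/AST >3xULN concurrent with total bilirubin > 2xULN (excluding Gilbert syndrome")) has its own exclusion and no PT/INR criterion. Table 11 governs dosing. In Section 7.2.3.2, item 2 applies to both arms without such exclusions. Item 3 is confined to the combination arm by design, and its part b has no PT/INR criterion. Different dosing rules for different drugs are expected.
- A reader might attach a count. Assuming that 2% to 8% of about 430 combination subjects (861/2) have PT/INR raised by an anticoagulant, and applying the Phase 1b laboratory ALT rate, gives 430 × 0.02 to 0.08 × 27/52 = 4.5 to 17.9. With the adverse-event rate of 18/52 it is 3.0 to 11.9. The prevalence has no source in the documents, and neither rate is filtered for causality.

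**Conclusion.** The conflict is real and should be fixed. Values that Table 4 and Section 5.6.2 accept are read as hepatic dysfunction in Table 8, item 3b(i) and Table 10 Scenario 1. The definition also uses total bilirubin, although item 2 says that the conjugated fraction is the informative one.

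The conclusion rests on a literal reading and on the ALT/AST rise being judged potentially drug-related. For rises up to 3xULN it also rests on Table 8 having no ALT/AST level of its own, and the consequence there is confined to axitinib. Above 3xULN the consequence is steroids and no rechallenge with either drug, whichever way Table 8 is read. The bilirubin route applies only at 2xULN or more. How many subjects are affected is unknown.

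A reader might infer a threat to the primary results, but the documents do not support that. Efficacy is analyzed by intention to treat, imaging continues after treatment stops, and discontinuation due to adverse events is summarized descriptively. The one efficacy analysis it could reach is PFS Sensitivity Analysis 2, which can count discontinuation of treatment as progression in subjects without documented PD or death.

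**What to change.** 1. Reconcile the hepatic-dysfunction definition in Table 8, Section 5.2.2.3.1 item 3b(i) and Table 10 Scenario 1 with Table 4, item 2 and Section 5.6.2. The text should say how PT/INR raised by permitted anticoagulation is to be read, and how total bilirubin raised with normal direct bilirubin is to be read.
2. Reconcile the ALT/AST entry level between the Table 8 row and Section 5.2.2.3.1, or state that the difference is intended.
3. Use one PT/INR cut-off in Table 8, item 3b(i) and the Table 10 scenarios, so that no value falls between them.

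Which reading and which cut-off apply is for the sponsor's clinicians to decide.

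The cost is wording in two tables and one list item, plus notice to sites. No new test is needed: the combination-arm flow chart already schedules PT/INR from Cycle 2 onward, and Table 14 requires direct bilirubin when the total exceeds ULN. Section 8.9 gives a final randomized number of 861, so enrollment is complete and the change can help only subjects still on combination treatment.
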